### **5.2 Participant Exclusion Criteria**

A potential participant who meets any of the following criteria will be excluded from participation in this study:

- DSM-IV diagnosis of alcohol or substance abuse (other than nicotine) within the last month or a DSM-IV diagnosis of alcohol or substance dependence (other than nicotine) within the last 6 months
- Medical or neurological illness (unstable cardiac disease, AIDS, malignancy, liver or renal impairment) or treatment for a medical disorder that could interfere with study participation
- History of traumatic brain injury that required subsequent cognitive rehabilitation, or caused cognitive sequelae
- A difference of greater than 20% in AHRS scores between Consent Visit and Screening Visit.
- Prior brain surgery
- Any brain devices/implants, including cochlear implants and aneurysm clips

- Co-morbid neurological condition (e.g. seizure disorder, brain tumor)
- Non English speakers
- Female participants who are pregnant, nursing, or unwilling to use an adequate method of contraception during study participation for those of childbearing potential.
- Anything that, in the opinion of the investigator, would place the participant at increased risk or preclude the participant's likelihood of completing all components of the study

### 5.3 Strategies for Recruitment and Retention

We intend to recruit 48 patients with schizophrenia and persistent auditory hallucinations, despite optimized antipsychotic medication treatment for at least 3 months. We will do this through both the UNC Hospital as well as the NCPRC Raleigh outpatient site, in coordination with providers at both locations. Additionally, we will also be contacting local ACT teams to recruit patients as well as potentially a small number from other community mental health providers. We estimate that approximately 10 subjects will be enrolled at the UNC-CH location, approximately 24 subjects will be enrolled at the Raleigh site, and approximately 14 subjects will be enrolled through ACT teams, for a total of 48 participants. Providers will be informed of the inclusion and exclusion criteria and will be asked to discuss the study with their patients at their next appointment or home visit in the case of the ACT team. Providers will include the medical teams treating patients at either of the two locations as well as the team that goes to see patients in the community through the ACT program. Providers will identify patients they believe to be appropriate for this study based on the information we will provide them about the study. Providers will ask patients whether they are willing to be contacted by the research team regarding participation. Providers will be asked to avoid unnecessary medication changes leading up to and over the 1 month course of the study.

Our retention strategy includes monetary compensation for the time and effort required to participate in the study. The participant will receive a payment at each session of the study. The research staff will also give each participant a reminder call for the initial screening session, each follow up screening session, the first day of stimulation, and each follow up session. Each research staff member will be easily available for the participants to contact via email or phone. The inclusion criteria state that each participant must be able to understand all risks and benefits associated with this study. We will be asking each participant to answer questions about the consent form to determine that the study process and the duration of participation are completely understood by all participants. We will aim to have a specific research team member assigned to complete all sessions with the same participant. However we will not require the same researcher to be present during stimulation sessions 2 through 4. The study team will work hard at forming a professional relationship with the participants so they feel comfortable and willing to discuss

what may be sensitive information. Retention will be quantified by participant attendance at each scheduled session (the data from each session will be scored and documented the day of the session. Participants will no longer be eligible to continue the study if they miss more than two non-consecutive sessions. Participants who miss two consecutive sessions will not be eligible to continue their participation.

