### **5.4.2 Reasons for Withdrawal**

A study participant will be discontinued from further participation if:

- The participant has missed more than 2 stimulation sessions.
- Any clinical adverse event (AE), laboratory abnormality, intercurrent illness or other medical condition, or situation occurs such that continued participation in the study would not be in the best interest of the participant.
- The participant meets any exclusion criteria (either newly developed or not previously recognized).
- A participant wishes to withdraw from further participation for any reason.

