### **5.4.3 Handling of Withdrawals**

We will collect safety data on any participant discontinued because of an AE or SAE. In any case, every effort will be made to undertake protocol-specified safety follow-up procedures. If voluntary withdrawal occurs, the participant will be asked to continue scheduled evaluations and complete an end-of-study evaluation. If an AE has been reported, researchers will help the participant seek the medical care they need and a follow up will be performed by the PI or Co-I. In the case of an early withdrawal, the

researcher will complete a Participant Off Study form to document the withdrawal reason (*Appendix Q*).

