### **6.3 Assessment of Participant Compliance with Study Investigational Product**

Compliance for this study includes making all 10 stimulation sessions allowing 2 non-consecutive miss which will be made up the following Saturday. Follow up periods will be able to take place  $\pm 3$  days of scheduled visits.

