## 7 STUDY SCHEDULE

Drs. [name], [name], [name] or other approved clinician will be present during the initial session, the 1st day of stimulation, the 5th day of stimulation, and the one month follow up for the first 5 participants, after which the approved clinicians will be present for only the initial session, the 5th day of stimulation and the one month follow up. The approved clinician will be present to administer the SAS (*Attachment 9*), the AIMS (*Attachment 7*) for each participant and the CGI-S (*Attachment 8*) for the first 5 participants until research personnel are comfortable and certified to do so (will be determined by accompanying clinician). In order to increase data quality, the assessments for an individual participant at the initial session, the 1st day of stimulation, the 5th day of stimulation, the one week one month follow ups will be administered by the same researcher. Protocol for this study will not require the same researcher to be present during days 2 through 4 of stimulation although the team will strive to schedule the same researcher for every session.

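### Removal for missed sessions ends study participation with no post-stimulation AHRS required, so some randomised participants can fall out of the primary comparison

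*Combined protocol and SAP*

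**What the plan says.** **Removal.** Section 5.3 sets two limits: "Participants will no longer be eligible to continue the study if they miss more than two non-consecutive sessions", and "Participants who miss two consecutive sessions will not be eligible to continue their participation". Section 5.4.2 opens "A study participant will be discontinued from further participation if" and lists as its first trigger: "The participant has missed more than 2 stimulation sessions". Section 6.3 describes compliance as "making all 10 stimulation sessions allowing 2 non-consecutive miss which will be made up the following Saturday".

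**Follow-up after removal.** Section 5.4.3 says: "If voluntary withdrawal occurs, the participant will be asked to continue scheduled evaluations and complete an end-of-study evaluation". For other discontinuations it promises safety data and safety follow-up. Section 9.1 names three safety assessments: vital signs, PANSS and the stimulation adverse effects questionnaire.

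**Primary analysis.** Sections 3.2.1 and 11.1.1 compare AHRS just before the first stimulation with AHRS just after the last. Section 11.3 analyses this with a mixed ANOVA having those two time points and three arms. Section 11 names no analysis population and no method for missing data.

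**The concern.** Appendix A marks randomisation in the same column as the first stimulation, so sessions missed after that are post-randomisation events. In this population they may be related to symptoms or to how well stimulation is tolerated. If missing sessions also costs a participant the primary outcome, the arms are compared among people selected by their behaviour after randomisation, and the protection of randomisation is weakened.

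The trial is a pilot, but preliminary efficacy on AHRS is part of its primary objective (Section 4), a between-group hypothesis is tested (Section 11.1.1), and a pilot is described as informing whether a large trial should follow (Section 11.2). With 16 per arm, each person lost is 1/16 = 6.25% of an arm.

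**Working it through.** The plan gives no attrition or missed-session figure, so there is nothing to reproduce. The check is a reading of the text followed by a count under stated assumptions.

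**Step 1: scope.** Both 5.3 and 5.4.2 refer to the study or to participation. Neither limits the consequence to stimulation.

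**Step 2: data after removal.** The request for continued evaluations in 5.4.3 is conditional on voluntary withdrawal, and AHRS is not a safety assessment in 9.1. No AHRS is required after an attendance removal, although nothing forbids one.

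**Step 3: analysis.** A classical two-time-point mixed ANOVA needs both scores. With no missing-data rule, a participant without the post score is omitted by default.

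**Step 4: the three attendance statements side by side.** *Session* is not defined. Section 6.3 counts 10 stimulation sessions, so there it means one stimulation. Section 5.3 writes "we will not require the same researcher to be present during stimulation sessions 2 through 4" where Section 7 writes "will not require the same researcher to be present during days 2 through 4 of stimulation", which supports a visit-day meaning.

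| Case | 5.3 | 5.4.2 | 6.3 |
|---|---|---|---|
| Session = stimulation; one whole day missed (2 consecutive) | removed | not listed (2 is not more than 2) | outside allowance |
| Session = visit day; two non-adjacent days missed (4 stimulations) | stays | removed | exceeds allowance |

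Staff could satisfy both rules by removing on either, but the plan does not say so.

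**Step 5: expected removals among 48.** From the plan: 48 participants, 16 per arm, five days with two stimulations each. Assumed: miss probability p = 0.02 / 0.03 / 0.05, independent between units. Only misses after the first stimulation, or whole days on Days 2 to 5, are counted unless stated.

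*A. Session = visit day, Days 2 to 5.*
- 5.3 (two adjacent days, or more than two): 3p²(1−p)² + 4p³(1−p) + p⁴. At p = 0.05: 0.00677 + 0.00048 + 0.00001 = 0.00725, × 48 = 0.35. Across p: **0.06 / 0.13 / 0.35**. Over all five days: 0.08 / 0.17 / 0.47.
- 5.4.2 (two or more days): 6p²(1−p)² + 4p³(1−p) + p⁴, giving 0.11 / 0.25 / 0.67. Every 5.3 removal is included, so removal on either rule is also 0.11 / 0.25 / 0.67.

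*B. Session = stimulation, single misses, 9 stimulations after the first.*
- 5.3 (two consecutive, or more than two): 8p²(1−p)⁷ + P(3 or more of 9). At p = 0.05: 0.01397 + 0.00836 = 0.02233, × 48 = 1.07. Across p: **0.16 / 0.37 / 1.07**. Over all ten: 0.19 / 0.44 / 1.27.
- 5.4.2: 0.03 / 0.10 / 0.40.

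*C. Session = stimulation, whole days missed, Days 2 to 5.*
- 5.3 (any missed day): 1 − (1−p)⁴ = 7.8% / 11.5% / 18.5%, × 48 = **3.7 / 5.5 / 8.9**.
- 5.4.2: 0.11 / 0.25 / 0.67.
- Absent on Day 5 only: 48p(1−p)³ = 0.9 at p = 0.02 and 2.1 at p = 0.05. These people lack a Day 5 score because they were away, whatever the rule. The remainder is 3.7 − 0.9 = 2.8 to 8.9 − 2.1 = 6.8.

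**The case against.** The strongest reply is that the attendance rule is a small part of a general omission. Any missing Day 5 AHRS, whether from an adverse event, refusal or loss to follow-up, has the same effect in 11.3. That is right, and the fix should cover all of these. The attendance rule still deserves its own correction, because there the plan itself ends participation for people who might have been willing to be assessed.

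A second reply is that few people are affected. Section 5.3 mostly uses *session* for a visit, and on that reading removals are below one of 48 at the assumed rates. Section 6.3 also tolerates two non-consecutive misses with a Saturday make-up. This stands and limits the size of the point. It does not settle the meaning, since 6.3 counts stimulations.

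Third, contact after removal is partly intended already: safety follow-up is promised in every case, and 9.1 places PANSS on the last stimulation day and at one month. This narrows the gap and makes the fix cheaper, but does not supply the AHRS.

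A reader might infer more than the documents support:
- *That the protocol prescribes an attenders-only analysis.* It does not. Omission is the default result of the named method without a missing-data rule, and nothing prevents collecting AHRS after removal.
- *That one missed day certainly removes a participant.* That holds only if a session in 5.3 is a single stimulation.
- *That a bias or an inflated type I error can be quoted.* Either would need removals by arm and the difference between removed and retained participants. The documents give neither.

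**Conclusion.** The concern holds in a limited form. As written, the plan can remove randomised participants for post-randomisation behaviour without requiring their primary outcome, and the planned ANOVA would by default omit them. The resulting risk is exclusion bias of unknown size and direction; no bias or power figure is claimed.

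Expected removals rest on an assumed 2% to 5% miss rate with independent misses. They are about one of 48 or fewer on the visit-day reading and for single missed stimulations. They reach about 4 to 9 of 48 only if sessions are stimulations and absences come as whole days, and 0.9 to 2.1 of those are Day-5-only absences. The undefined term and the pattern of absence drive the result. The correction should be made because it is cheap and the affected number cannot be bounded from the plan; confidence in its practical weight is medium.

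**What to change.** 1. Define *session* and state one attendance rule, identical in 5.3, 5.4.2 and 6.3. The sponsor may keep its limit on consecutive misses.
2. State that breaching the rule ends stimulation only.
3. Extend the 5.4.3 request for continued evaluations to every randomised participant who has not withdrawn consent, with AHRS at the existing Day 5, one-week and one-month visits. This also covers people discontinued for adverse events.
4. In 3.2.1, 11.1.1 and 11.3, define the primary post score as the AHRS at the scheduled end of the stimulation week (Day 5, or after the Saturday make-up session), whether or not stimulation was completed. Without this, the score after the last stimulation has no clear meaning for someone who stops on Day 2.
5. Analyse all randomised participants in their assigned arms, for example with a likelihood-based mixed model using all AHRS visits, and report completers as a sensitivity analysis.

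The cost is protocol and analysis wording, a few extra assessments and payments at visits already scheduled, and a small change in endpoint timing for early stoppers. A Day 5 score missing because the participant was absent may not be recovered; the later AHRS visits would then carry the information.

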## **5.4 Treatment Assignment Procedures**

Participants will be randomized into one of three arms. This is a double blind study, so neither the participant nor the researcher will know which treatment arm the participant has been assigned to.

### **5.4.1 Randomization Procedures**

A [name] Lab member will randomize 48 codes which will be used by the study coordinator and research assistants. These codes are directly linked to which treatment participants receive (sham, 10Hz tACS or 2 mA tDCS). This lab member will have no other responsibility in the study other than providing these randomized codes.

### **5.4.2 Reasons for Withdrawal**

A study participant will be discontinued from further participation if:

- The participant has missed more than 2 stimulation sessions.
- Any clinical adverse event (AE), laboratory abnormality, intercurrent illness or other medical condition, or situation occurs such that continued participation in the study would not be in the best interest of the participant.
- The participant meets any exclusion criteria (either newly developed or not previously recognized).
- A participant wishes to withdraw from further participation for any reason.

### **5.4.3 Handling of Withdrawals**

We will collect safety data on any participant discontinued because of an AE or SAE. In any case, every effort will be made to undertake protocol-specified safety follow-up procedures. If voluntary withdrawal occurs, the participant will be asked to continue scheduled evaluations and complete an end-of-study evaluation. If an AE has been reported, researchers will help the participant seek the medical care they need and a follow up will be performed by the PI or Co-I. In the case of an early withdrawal, the

researcher will complete a Participant Off Study form to document the withdrawal reason (*Appendix Q*).

#### **5.4.4 Termination of Study**

This study may be prematurely terminated if, in the opinion of the investigator, there is sufficient reasonable cause. Circumstances that may warrant termination include, but are not limited to:

- Determination of unexpected, significant, or unacceptable risk to participants.
- Insufficient adherence to protocol requirements.
- Data those are not sufficiently complete and/or evaluable.
- Plans to modify suspend or discontinue the development of the study device.

The IRB will be informed promptly and provided the reason(s) for the termination or suspension by the sponsor or by the investigator/institution, as specified by the applicable regulatory requirement(s).

## **6 STUDY INVESTIGATIONAL PRODUCT**

### **6.1 Study Product Description**

We will be using a transcranial current stimulator designed in the [name] Lab for investigational research purposes. The device is not implanted and has not been designed for or being used to support or sustain human life. This device does not have a potential for serious risk to the health, safety, or welfare of the participant. There has never been an instance of serious side-effect reported due to use of transcranial brain stimulation. Previous studies in the [name] Lab that used comparable devices have always been classified as “non-significant risk” by the UNC IRB.

In addition, some participants will be stimulated with the commercial, CE-certified Neuroconn Plus stimulator (for purely logistic reasons of device availability). The use of this device in this study has previously received a NSR designation on initial review by the full UNC IRB. Both devices are electrically equivalent and provide the same stimulation. The NeuroConn device description is as follows:

The DC-STIMULATOR is a CE-certified medical device for conducting non-invasive transcranial direct-current stimulation (tDCS) in humans. DC stimulation is used in clinical practice and in the research of stroke, epilepsy, migraine, tinnitus, depression, multiple sclerosis, dementia and chronic headache. The DC-STIMULATOR is a micro-processor-controlled constant current source. It meets the highest safety standards thanks to (hardware- and software-based) multistage monitoring of the current path. By continuously monitoring electrode impedance it can detect insufficient contact with the skin and automatically terminate stimulation, maximising patient safety.

The device's alphanumeric display and the 4 touch keys allow various stimulation modes to be selected and stimulation parameters such as current strength, duration, fade-in and fade-out to be set.

DC-STIMULATOR features:

- 1 channel (anodal and cathodal stimulation possible)
- Adjustable current up to 5,000  $\mu$ A \*
- Adjustable application time up to 30 minutes \*
- 2 standard modes - single (continuous stimulation) and - pulse (cyclical stimulation activation/deactivation) with fade in and fade out
- Customer-specific programs possible (optional)
- "Study mode" for blind processing of genuine and 'pseudo' stimulation (optional)
- External trigger input (optional)

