## 6.2 Preparation and Administration of Study Investigational Product

After participants have completed the daily questionnaires, they will be comfortably seated. The research team will first measure their heads electrode placement using the 10-20 system. Participants will then be fitted with the 3 electrodes for stimulation. The participant will be in the

relaxed yet, experimentally controlled state by watching a nature movie. One session of stimulation will be performed twice daily, for 20 minutes. In the 10 Hz tACS and 2mA tDCS groups stimulation will have a 10 second ramp in and ramp out with 20 minutes of stimulation for a total of 1220 seconds. Stimulation waveforms are sine-waves with a peak-to-peak amplitude of 2 mA. The sham stimulation will include 10 seconds of ramp in to 1 minute of 10 Hz tACS with a ramp out of 10 seconds for a total of 100 seconds of stimulation. We will be using 5x5cm electrodes covered in 10/20 conductive paste and placed between Fp1 and F3 and between T3 and P3 with a 5x7cm electrode placed over CZ as a return electrode.

Stimulation devices will be preprogrammed and codes will be randomized to one of the three experimental arms. Researchers will enter the participant-specific code into the App that controls the stimulation and monitor participants during the 20 minutes of the stimulation.

The study coordinator and/or the research assistant will be thoroughly trained and have trainings documented on the transcranial stimulation device and will be present during all stimulation sessions. *Please see Appendix S for an example of the training documentation log.* To monitor side effects of stimulation a daily questionnaire will be administered after each stimulation session. *Please see Attachment 1 for an example of the daily stimulation questionnaire, and Attachment 2 for an example of the endpoint stimulation questionnaire.*

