## **10 CLINICAL MONITORING**

The Purpose of the monitoring plan is to present the [name] Lab's approach to monitoring clinical trials. The plan facilitates compliance with good clinical practice.

- (a) The rights and well-being of human subjects are protected.
- (b) The reported trial data are accurate, complete, and verifiable from source documents.
- (c) The conduct of the trial is in compliance with the currently approved protocol/amendment(s), with GCP, and with applicable regulatory requirement(s).

This section identifies key monitoring activities and specifies the data to be reviewed over the course of a clinical trial. This is a single site, investigator initiated, clinical trial so there will be no site monitoring plan in place.

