Excellent! Due to the study schedule, some sessions will be longer than others. Is it possible for you to be available from 8 – 5 on weekdays to be at the UNC Hospital in order to participate in this study? If not, can you specify the days/times that do not work for you?

Would you be willing to participate in an 8 hour session for this study? (This includes a 3 hour break).

You are eligible for participation in the first session of the study. At the first session we will determine your eligibility for the remainder of the sessions. I'd like to schedule your first session now. It will last approximately 3 hours. All testing will be conducted at either UNC Hospital or the NCPRC in Raleigh. (specific location).

(Schedule a time for first session)

I will give you a call to confirm your appointment 24 hours beforehand. If you have any questions before then, please don't hesitate to contact us at this phone number.

Thank you for your time.

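### The commercial stimulator, used when availability dictates, is called equivalent to the lab device but described as a one-channel DC unit with no stated masking route, so its use could reveal the tDCS arm and confound device with it

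*Combined protocol and SAP*

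**What the plan says.** Section 6.1 introduces a lab-built stimulator and then adds a second one: "some participants will be stimulated with the commercial, CE-certified Neuroconn Plus stimulator (for purely logistic reasons of device availability". It gives no number of participants and no rule other than availability. It asserts that "Both devices are electrically equivalent and provide the same stimulation".

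The device text that follows reads "The DC-STIMULATOR is a CE-certified medical device for conducting non-invasive transcranial direct-current stimulation (tDCS) in humans". The feature list begins with "1 channel (anodal and cathodal stimulation possible" and gives two standard modes, continuous and pulsed on/off. It lists no sine-wave mode and no frequency setting. Customer-specific programs and a blinded study mode (genuine versus pseudo stimulation) appear only as options, and the protocol does not say that either is used. Modes and parameters are set with keys and a display on the unit itself.

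Section 6.1.1 lists the lab device's settings, which include a tDCS/tACS choice, the number of channels and a tACS frequency. The tablet App is one of its components. Section 6.2 says "Participants will then be fitted with the 3 electrodes for stimulation": two active electrodes and a return over Cz. It masks treatment through preprogrammed devices and a participant code that the researcher enters in the App.

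Section 4 defines sham as one minute of 10 Hz tACS between ramps. Section 5.4 says that participant and researcher are both blind to arm. Section 14.1 gives questionnaire administration and device administration to the same staff. The Protocol Summary calls tDCS versus sham the positive control for assay sensitivity.

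**The concern.** Two of the three arms, tACS and sham, need 10 Hz alternating current. Read literally, the commercial unit's description supports only the third. If that is the unit in use, availability cannot be what decides who gets it. A blinded operator who picked it for a participant with a tACS or sham code could not deliver the session. Either the arm must be known when the device is chosen, or a device swap discloses it.

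Two things would then be at stake. The first is blinding. The primary outcome, the AHRS, is an interview rating, and section 7 wants one researcher to do a participant's key assessments. That researcher may also be the person operating the device, and so would know the arm of every participant on the commercial unit. The second is confounding: every user of the unit would be in the tDCS arm, so any difference between devices would enter the tDCS-versus-sham comparison. That comparison is how the trial would judge whether a null tACS result reflects the treatment or an insensitive assay.

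Even if the unit can produce AC, the protocol gives no masking route for it.

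**Working it through.** The plan states no figure for device balance, so there is nothing to reproduce. The first step compares the sections; the rest is illustrative arithmetic. The number of participants on the commercial unit, k, is not given and is assumed throughout.

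**1. Requirements against description**

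| Requirement | Lab device (6.1.1, 6.2) | Commercial unit (6.1) |
|---|---|---|
| 2 mA tDCS arm | tDCS selectable | Described purpose of the unit |
| 10 Hz tACS arm | tACS with frequency setting | No AC mode or frequency listed; custom programs optional |
| Sham (1 minute of 10 Hz tACS) | As above | As above |
| Three-electrode montage | Channel number selectable | One channel; lead arrangement not stated |
| Arm hidden from operator | Code entered in the App | Display and keys; study mode optional, genuine versus pseudo only |

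**2. Unblinding if the unit is DC only**

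All k users are then in the tDCS arm. From 48 participants at 16 per arm:

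- P(tDCS | commercial unit) = 1.
- P(tDCS | lab device) = (16 − k)/(48 − k). For k = 4, 8, 12 and 16 this is 12/44 = 0.273, 8/40 = 0.200, 4/36 = 0.111 and 0/32 = 0. The value with no information is 16/48 = 0.333.

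Seeing the commercial unit therefore identifies the arm with certainty. Seeing the lab device makes tDCS less likely. For comparison, if device were independent of arm, the probability that all of 4 users fell in tDCS would be C(16,4)/C(48,4) = 0.009.

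**3. Bias in tDCS versus sham if the unit is DC only**

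Sham runs entirely on the lab device, and k of the 16 tDCS participants use the other one. A device effect of δ SD on AHRS change shifts the comparison by δ × k/16.

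Take δ = 0.5 (assumed), a two-sample t-test with 16 per arm (30 degrees of freedom) and two-sided 5% (assumed; section 11.3 states no alpha). The noncentrality is 0.5 × (k/16) × √(16/2).

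| k | Shift (SD) | Noncentrality | False-positive rate |
|---|---|---|---|
| 4 | 0.125 | 0.354 | 0.064 |
| 8 | 0.250 | 0.707 | 0.105 |
| 12 | 0.375 | 1.061 | 0.177 |
| 16 | 0.500 | 1.414 | 0.278 |

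This covers a device effect only; rater bias from unblinding would be additional and is not quantified. tACS and sham would both run on the lab device, so that contrast carries no device shift.

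**4. If the unit serves all three arms and the choice is blind to arm**

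Only chance imbalance remains. With 6, 12, 18 or 24 of 48 on the unit (assumed), the hypergeometric probability that tACS and sham differ by 4 or more users is 0.06, 0.16, 0.21 or 0.22. This costs precision; it is not bias.

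**The case against.** The strongest reply is that confounding is conjectured. If the researcher is blind (section 5.4), the devices are preprogrammed (section 6.2) and availability alone decides, then device is independent of arm and imbalance is chance. The description may also be incomplete. Section 6.1 names one model and describes a unit under another name, and optional custom programs could include a sine wave. This stands as far as it goes: a reader might infer that the unit cannot deliver AC and that device and arm are therefore confounded, and the documents do not establish that. It does not remove the contradiction within section 6.1 or supply a masking route for the commercial unit.

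One channel against three electrodes might be read as an incompatibility. It is not shown to be one, because the protocol does not say how channels map to electrodes and a split lead is not excluded.

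A reader might also extend the point to location. Appendix S says "All testing will be conducted at either UNC Hospital or the NCPRC in Raleigh", section 5.3 expects about 24 of 48 from Raleigh, and section 5.4.1 describes no split of the codes. But the Protocol Summary and sections 4 and 10 say single site, the 24 is a count by enrolment source, and no testing place is given for the 14 expected through ACT teams. If 24 codes were used at one location, tACS and sham would differ there by 4 or more with probability 0.22, and some pair of arms would with probability 0.43. Those are chance imbalances under valid randomization, not bias or an inflated error rate.

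**Conclusion.** The point holds in limited form. Section 6.1 contradicts itself: it asserts that the devices give the same stimulation, and describes one for which only tDCS is clearly deliverable. The only masking route belongs to the other device, and the same staff rate and operate. Followed as written, the plan can unblind the AHRS rater and tie device to the tDCS arm.

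The size is conditional. If the unit is DC only, the arm is known for all k of its users, and the false-positive rate for tDCS versus sham rises from 5% to between 6.4% (k = 4) and 27.8% (k = 16) under an assumed 0.5 SD device effect. Neither k nor the device effect is in the documents. tACS versus sham is largely spared. If the unit delivers all arms and is masked, the systematic problem disappears and only chance imbalance is left. The repair should be made before enrolment, because no analysis restores masking once ratings have been made unblinded.

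**What to change.** - **Section 6.1:** reconcile the equivalence sentence with the device description. State which arms each device delivers in the three-electrode montage, with verification of output.
- **Sections 6.1 and 6.2:** allow the commercial unit only if it delivers all three arms through a preprogrammed code that hides the arm from the operator. The listed study mode is not enough as described, since it covers only genuine versus pseudo stimulation. Otherwise use the lab device for everyone and delete the equivalence sentence.
- **Section 5.4.1:** fix each participant's device before the code is opened.
- **Data capture and section 11.3:** record device and testing location and report both by arm. If both devices serve all arms, add device as a covariate in a sensitivity analysis. If the unit served only tDCS, such adjustment would rest on a non-randomized comparison within one arm and would not solve the problem.
- **Location:** resolve Appendix S against the single-site statements. If there are two testing locations, blocking the codes by location is an optional gain in precision.

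The cost is a clarified device section, an output check and two recorded fields. The small downside is less freedom to swap devices.
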